#### 1. All Enrolled Population:

The all-enrolled study population is defined as those individuals who signed an informed consent, and were subsequently randomized in the study (this population includes both the evaluable and the non-evaluable patient samples). The reasons for patient non-evaluability will be itemized in the final study report, however, no other summary statistics of demographics or clinical outcomes will be reported for the all-enrolled study population. This population will constitute the safety analysis dataset.

#### 2. Intent-to treat/Evaluable:

The intent-to-treat study population (also known as the evaluable patient population) is defined as all subjects who signed an informed consent, were enrolled in the study and received at least one treatment (whether partial or complete), and for whom a complete post-baseline observation is available for analysis in Phase I.

#### 3. Per-protocol:

The per-protocol study population (also known as the completer population) is defined as all subjects who signed an informed consent, were enrolled in the study, who met inclusion/exclusion criteria, completed all efficacy assessments at Week 4 or Week 6, and received at least 30 treatments within 6 weeks of treatment initiation of the Phase I acute treatment.

The per-protocol study population 2 is defined as all subjects who signed an informed consent, were enrolled in the study, who met inclusion/exclusion criteria, completed all efficacy assessments at week 4 or week 6, and met the protocol requirements treatment compliance. The protocol defines treatment compliance as a subject cannot miss  $\geq$ 3 treatments in daily sequence or be missing more than 20% of the total number of treatment sessions occurring during the 6 weeks of acute treatment (does not include taper treatments) in either Phase I or Phase II

To satisfy the requirements and definitions of the original study SAP, analyses of the effectiveness outcomes will be performed using per-protocol study population 1, however, the results from per-protocol population 2 will be considered the primary per-protocol analyses for the study given per protocol treatment regimen.

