17.3 Case Report Forms

The Sponsor will provide case report forms (CRFs) for each subject enrolled into the study to ensure consistent data collection.

Data will be captured at each participating site by qualified study staff who will perform primary data collection from source-document reviews to case report forms (CRF). Data will be collected for this study utilizing one or a combination of the following-methods:

- 1. Data may be transcribed from the Electronic Medical Record (EMR-an electronic source-that must be available for review) onto the CRF. A copy of the EMR will be printed and placed in the subjects case file as source documentation.
- 2. Data may be captured directly onto the CRF and transcribed into the EDC system by Neuronetics, BUT paper documentation must be retained and available for review.

Data reported in the CRF should be consistent with the source documents or the discrepancies should be explained.

Data Management

Neuronetics and/or Study Sites will enter data from the CRFs into an electronic data capture (EDC) system that is compliant with 21 CFR (Code of Federal Regulations) Part 11 FDA (Food and Drug Administration) requirements. Edit checks, electronic queries, and audit trails are built into the system to ensure accurate and complete data collection and security. Data will be transmitted via the internet to a central hosting site, utilizing state-of-the-art encryption mechanisms to ensure security and confidentiality.

Details of the study treatments including treatment parameters, such as MT for each subject, will be retained within the TMS device by the XPLOR software. In addition, a printed report of the treatments

Page 48 of 61

will be stored as part of the subject's source documents. Details from the study treatments will be entered into EDC.

Case files will be created for each subject where completed CRFs will be stored.

Data Security and Confidentiality

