### 1. Phase I (Randomized, Blinded):

For subjects randomized to the active treatment, stimulation will occur at a maximum of 120% magnetic field intensity relative to the subject's resting motor threshold (MT), at 10 pulses per second (10 Hz) for 4 seconds, with an intertrain interval of 26 seconds. Repositioning of coil, per NeuroStar User Manual, and prophylactic use of acetaminophen or ibuprofen will be allowed for subjects reporting sensations at or near the stimulation site which are uncomfortable. During the first week of treatment only, in the event that the subject cannot tolerate the treatment at these dose parameters, dose intensity may be titrated downward to 110% of the motor threshold, with all other dose parameters remaining the same. Treatment sessions will last for 37.5 minutes (75 trains) to provide a total of 3,000 pulses per treatment session. A maximum total of 36 treatments will be completed within 9 weeks of Phase I (including the 6 treatments administered during the 3-week taper phase). If the subject meets criteria (blinded to Site personnel) to enter Phase II, they will not complete the 3-week taper phase, resulting in a maximum total of 30 treatments.

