## **B.** Primary and Secondary Outcomes:

Table 6. Summary of Primary and Secondary Efficacy Study Measures, Prioritized Order of Analysis, and General Definitions of Outcome Measures

Primary Efficacy Outcome Measure	Definitions
HAMD24: total score, intent to treat	HAMD24 total score change from baseline value through
sample using last post-treatment score	week 6
Secondary Efficacy Outcome Measures	Definitions
Continuous outcomes HAMD17, HAMD24 (per protocol), MADRS, CDRS-R, QIDS-A17-R, CGI-S: total score, intent to treat sample using last post-treatment score	For each indicated measure, total score change from baseline value through week 6
Responder categorical outcome HAMD (24 and 17 Item versions) MADRS CDRS-R QIDS-A17-SR CGI-S	For HAMD, MADRS, CDRS-R, and QIDS-A17-SR: proportion of patient population achieving an end of acute phase total score reduction of $\geq$ 50% compared to baseline score
	For CGI-S: End of acute treatment score of 1, 2 or 3.
Factor scores derived from the HAMD including (using the last post-treatment value)	
Anxiety/Somatization	Anxiety/Somatization (sum of items 10, 11, 12, 13, 15, 17)
Core Factor	Core Factor (sum of items 1, 2, 3, 7, 8)
Maier	Maier (sum of items 1, 2, 7, 8, 9, 10)
Gibbons	Gibbons (sum of items 1, 2, 3, 7, 9, 10, 11, 14)
Retardation	Retardation (sum of items 1, 7, 8, 14)
Sleep	Sleep (sum of items 4, 5, 6)
Remitter categorical outcome	
HAMD (24 and 17 Item versions)	For HAMD24: End of acute treatment score < 11
MADDC	For HAMD17: End of acute treatment score < 8
MADRS	For MADRS: End of acute treatment score < 10
CDRS-R	For CDRS-R: End of acute treatment total score < 28
CGI-S	For CGI-S: End of acute treatment score 1 or 2

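### Both per-protocol sets accept complete ratings at Week 4 or Week 6, but the per-protocol HAMD24 outcome is a Week 6 change, so a carried-forward Week 4 score can stand in for it

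*SAP*

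**What the plan says.** SAP Section 3.C.3 gives two definitions. Population 1, "also known as the completer population", requires consent, enrolment and eligibility, that the patient "completed all efficacy assessments at Week 4 or Week 6", and that the patient "received at least 30 treatments within 6 weeks of treatment initiation of the Phase I acute treatment". Population 2 requires the same entry conditions and that the patient "completed all efficacy assessments at week 4 or week 6, and met the protocol requirements treatment compliance". Compliance there means fewer than 3 sessions missed in sequence and no more than 20% of sessions missed, the rule in Protocol 14.2. The SAP names population 2 as the primary per-protocol set.

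SAP Table 6 (Section 7.B) defines the primary outcome as "HAMD24 total score change from baseline value through" Week 6. It lists per-protocol HAMD24 first among the secondary outcomes, in the group of continuous measures, over the same interval and with the last post-treatment score. SAP 3.E carries a Week 4 score forward when the Week 6/early-termination score is missing, and it sets a visit total to missing if any item is missing. Neither rule is switched off for the per-protocol sets. SAP Section 4 gives the per-protocol population a supporting role; the intent-to-treat population is primary.

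**The concern.** A per-protocol result is read as the result in patients who were treated and assessed as planned. Here the entry rule and the outcome refer to different visits. The word *or* lets in patients who lack the Week 6 score that the outcome needs, and carry-forward then fills the gap without any sign of it in the output. The word *all* works the other way: it ties the HAMD24 analysis to the completeness of MADRS, CDRS-R, CGI-S and QIDS-A17-SR, which have no bearing on whether HAMD24 was measured.

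What is at stake is how the per-protocol HAMD24 analysis can be read, as a named secondary outcome and as support for the primary. The primary analysis and the three success criteria in SAP 2.D do not use it.

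**Working it through.** **1. The plan's own figures.** A full course is 30 sessions. Each session is 75 trains × 10 pulses/s × 4 s = 3,000 pulses, lasting 75 × (4 + 26) s = 37.5 min, as the Protocol and SAP state. The 20% limit allows 0.20 × 30 = 6 missed sessions, so population 2 admits patients with 24 or more sessions.

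**2. What the rules do with four patients.** All meet the eligibility and session criteria.

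| Patient | Week 4 | Week 6 | In the sets? | HAMD24 value used |
|---|---|---|---|---|
| A | all scales complete | all scales complete | yes | Week 6, observed |
| B | all scales complete | HAMD24 missing, or one item missing | yes | Week 4, carried forward |
| C | HAMD24 valid, another scale incomplete | HAMD24 valid, another scale incomplete | no | none; an observed Week 6 score is discarded |
| D | visit missed | all scales complete | yes | Week 6, observed |

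B and C are the two faults. C assumes that a scale with a missing item does not count as completed, which is the natural reading beside SAP 3.E.

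**3. How B can arise.** Population 1 patients have all 30 sessions. Population 2 patients may miss at most 2 in a row, so their last session is at slot 28 or later, which is in Week 6 (slots 26 to 30 at five a week). Early dropout therefore does not produce patient B. A missed Week 6 rating or an incomplete HAMD24 does, and this should be uncommon. The documents give no rate.

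**4. Size.** Let q be the share of the set, equal in both arms, with only a Week 4 score. Suppose the active–sham difference grows linearly from zero at baseline to its full value at Week 6. The Week 4 difference is then 4/6 = 2/3 of the Week 6 difference, and the estimate is multiplied by

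(1 − q) + q × 2/3 = 1 − q/3.

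- q = 3%: 1 − 0.010 = 0.990, an attenuation of 1.0%.
- q = 10%: 1 − 0.033 = 0.967, an attenuation of 3.3%.

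The SAP cites adult HAMD24 differences of 1.7 to 2.5 points. On that scale the shrinkage runs from 1.7 × 0.010 = 0.02 to 2.5 × 0.033 = 0.08 points. Both q and the linear shape are assumptions.

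**5. Delivered dose.** Neither definition mentions pulses or intensity. By count alone, population 2 runs from 24 × 3,000 = 72,000 to 30 × 3,000 = 90,000 pulses if every session is full length, and nothing in the definition checks that. Protocol 17.3 says "Details from the study treatments will be entered into EDC", so a summary is feasible. The rows that can be read in the SAP Section 6 table are motor-threshold summaries.

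**The case against.** The case for leaving the text alone is fair in several respects. The Week 6 effect is small by any plausible count. Protocol 11.5 asks early discontinuers for Week 6 procedures within 2 days of the last session, and the session criteria keep early dropouts out. SAP 2.B plans an observed-case analysis, and SAP 3.E allows a sensitivity analysis. All of this stands and limits the size of the point. It does not remove it: the observed-case analysis is not tied to the per-protocol sets, the sensitivity analysis is optional, and neither restores patient C.

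A reader might go further and infer that the sets retain under-dosed active patients, that this pulls the active arm toward sham, and that short or low-intensity sessions should be grounds for exclusion. The documents do not support this, for five reasons.

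- Population 2 applies the protocol's own adherence rule, which counts sessions.
- The words "received at least one treatment (whether partial or complete" occur only in the intent-to-treat definition. Their absence from 3.C.3 leaves the per-protocol meaning open; it does not show that partial sessions count there.
- The intensity text is not uniform. Protocol 10.1 specifies 120% of motor threshold. Protocol 13.1 and SAP 3.A.1 make 120% a maximum, and 13.1 makes the return to it subject to tolerance by the end of the first week. The reduction rule begins "During the first week of treatment only, in the event that the subject cannot tolerate the treatment at these dose parameters". These sections must be reconciled before anyone can say who departed from them.
- Application site pain in the adult trial (59/165 = 35.8% active, 6/158 = 3.8% sham; Protocol Table 1) is a pain rate, not an under-dosing rate. A dilution factor 1 − u(1 − r), with share u under-dosed and fraction r of benefit kept, gives 0.95 at u = 10%, r = 0.5 and 0.70 at u = 30%, r = 0. No value of u or r is in the documents.
- If pain on active treatment did drive under-dosing, excluding those patients would remove poor tolerators after randomisation, mainly from one arm, and could favour the device.

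**Conclusion.** The mismatch between the entry rule and the outcome is real and follows from the text. Both per-protocol sets can include patients whose Week 6 HAMD24 is a carried-forward Week 4 score, and both can exclude patients whose HAMD24 data are complete. The expected attenuation is about 1% to 3%, assuming 3% to 10% of the set have only a Week 4 score, equal shares in the two arms and linear growth of benefit. It bears on a supportive analysis and changes no success criterion. Only population 1 carries the completer label, and it does require all 30 sessions, so the two sets should not both be described as completers.

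That neither set considers delivered dose is a gap in description. It does not establish that the per-protocol estimate is diluted, and it does not justify exclusion by dose.

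**What to change.** In both definitions in SAP 3.C.3, replace the condition on efficacy assessments with *a complete baseline and Week 6 score on the scale being analysed*. State in 3.E that no value is carried forward in the per-protocol analyses.

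For each per-protocol set, add a table by arm of delivered pulses and intensity from the treatment data in EDC, for description only. The sponsor should also reconcile the intensity wording in Protocol 10.1, Protocol 13.1 and SAP 3.A.1, so that the table can be read against one stated regimen.

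The cost is a short SAP amendment before database lock, a change to the population flags and one extra table. The per-protocol set becomes slightly smaller where Week 6 scores are missing and differs a little from scale to scale, so the number analysed must be shown with each outcome. The intent-to-treat analysis is unchanged.

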11.3 Exclusion Criteria

Table 3 – Exclusion Criteria

Exclusion Criteria	Determinant
Subjects directly affiliated with the study or their immediate families (parent or sibling, whether by birth or legal adoption)	Physician interview
Subjects currently on concurrent medication listed as excluded on the Concomitant Medication list (Appendix D) and/or use of an investigational drug within 4 weeks of the baseline visit.	Physician evaluation and review of medical record
Active substance use	Urine drug test (at screening; second test allowed prior to randomization as permitted by Sponsor)
Prior TMS, vagus nerve stimulation (VNS), or ECT	Medical history
Contraindication to MRI (only for Structural Head MRI subset subjects)	Physician evaluation; medical history; MRI Safety Screening Questionnaire

Contraindication to TMS	Physician evaluation and review of
Conductive, ferromagnetic, or other magnetic-sensitive metals implanted in the subject's head within 30 cm of the treatment coil excluding the mouth that cannot safely be removed. Examples include cochlear implants, implanted electrodes/stimulators, aneurysm clips or coils, stents, bullet fragments, jewelry and hair barrettes.	medical record
Active or inactive implants (including device leads), including deep brain stimulators, cochlear implants, and vagus nerve stimulators.	
Cardiac pacemakers, implanted medication pumps, intracardiac lines	Physician evaluation and review of medical record
A true positive response to any question on the TASS questionnaire	Physician evaluation
History of neurological disorder or insult including but not limited to the following that may increase risk of seizure:	Physician evaluation and review of medical record
 Antecedent seizures Any condition likely to be associated with increased intracranial pressure Space occupying brain lesion History of cerebrovascular accident Transient ischemic attack within 2 years Cerebral aneurysm Dementia Brain surgery Head trauma with loss of consciousness for ≥5 minutes History of stroke History and/or family history of epilepsy Unstable medical conditions, including: Hematological or infectious (e.g., human immunodeficiency 	Physician evaluation; medical history

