14.2 Subject Compliance Monitoring

Non-adherence to the assigned treatment regimen is defined as missing ≥ 3 treatments in daily sequence, or missing more than 20% of the total number of treatment sessions occurring during the 6 weeks of acute treatment (does not include taper treatments) as outlined in the schedule of events (i.e., 100% compliance = 30 total treatments). However, if the subject does miss a treatment, the subject must not go more than 3 calendar days without a treatment session. Treatments missed during the taper visits are considered protocol deviations. Subjects who are unable to comply with this schedule may be withdrawn from the investigational treatment portion of the study. If a subject receives more than the prescribed number of pulses (i.e. 3000 pulses of good contact), this would be considered an overdose and documented on the SAE form and reported to Neuronetics.

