14.3 Prior and Concomitant Therapy

Reasonable efforts will be made to determine all somatic therapies for depression received by the subject in the past 2 years. All other medications and therapies received within six months of study enrollment will also be determined. All relevant information will be recorded on the subjects CRF. The ATR will be used in this study to verify the inclusion criteria pertaining to treatment resistance and intolerance. (See Study Reference Manual for details of the administration of the ATR.)

Permitted Concomitant Therapy

Zaleplon, zolpidem, or zopiclone (1 dose nightly) as needed for treatment emergent insomnia or lorazepam (up to 2 mg daily) for treatment emergent anxiety, may be administered for up to 14 doses during Phase I and an additional 14 doses during Phase II. For Phase III, these medications may be administered for up to 10 days, on \leq 5 occasions. The use of alternative hypnotics or anxiolytic compounds requires prior approval from the Sponsor. Hormonal contraceptives are allowed if the subject has been on a stable dose for at least 3 months. Short-term treatments for headaches, allergies, colds, and flu symptoms will be allowed during the study provided the medications utilized have no established psychotropic effects that would be expected to confound interpretation of study outcome measures. These medications may include non-sedating, over-the-counter, or prescription antihistamines, analgesics and decongestants. All questions regarding the acceptability of specific medications must be approved by the Sponsor.

[figure not shown]
Page 37 of 61

CONFIDENTIAL

Prohibited Concomitant Therapy

Any medication administered for the treatment of any psychiatric or neurologic disorder or any other known CNS active drugs, including herbal, over-the-counter, and homeopathic medications, MAOIs, other antidepressants, antipsychotics, stimulants and mood stabilizers are prohibited during this study (See Appendix D, Concomitant Medication Exclusion List). Use of Zaleplon, zolpidem, zopiclone or lorazepam for more than the permitted days (see above) or beginning a new regimen of hormonal contraception may lead to excluding the subject from the study.

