#### A. Trial Design Summary:

Study 44-02219-000 is a multi-center, randomized, sham-controlled clinical trial evaluating the safety and effectiveness of treatment with the NeuroStar TMS Therapy system in adolescent patients ages 12 through 21 who have failed to received treatment benefit from prior administration of antidepressant medications. The study is organized into 3 separate phases. During Phase I, patients meeting inclusion and exclusion criteria are randomly assigned in a 1:1 ratio to receive either daily treatment with the NeuroStar TMS Therapy device in the XPLOR research configuration or sham NeuroStar treatment for up to 6 weeks (30 treatments). Patients who do not meet criteria for clinically significant treatment benefit are offered the opportunity to enter Phase II, where open-label active NeuroStar TMS Therapy is provided to all patients for up to 6 weeks (30 treatments). Patients who receive clinically significant treatment benefit at the conclusion of either Phase I or Phase II are offered the opportunity to proceed into Phase III, where NeuroStar TMS Therapy is tapered, and patients are continually monitored for up to 6 months to determine the durability of effect of benefit from the acute treatment phases of the study. All patients are treated with NeuroStar TMS Therapy as a monotherapy, no antidepressant medications are permitted during the course of all three study Phases. During Phase III, patients are permitted to receive a reintroduction of an acute course of NeuroStar TMS Therapy if they meet protocol-defined criteria for symptom re-emergence.

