## Section 9. Other Analyses

## A. Concomitant Medications:

A listing of all permitted concomitant medications used will be provided, including a listing of the proportion of patients who received any concomitant medications listed on the Excluded Medications List.

Subjects were allowed to take non-psychotropic medications and limited medications for sleep and breakthrough anxiety medications. These medications were all to be clearly documented regarding dates of administration, not just dates of prescription. Psychotherapy was allowed if consistent in focus and frequency throughout study. Other non-behavioral or psychological therapies were allowed.

Table 10.	Descrip	otive ir	nclusion	of medi	cations	and o	other	therap	pies	should	be i	included b	y group	in all
phases.	_							-	-					

Variable Name	Туре	Items
Concomitant psychotropic		
medication		
Anxiolytic	Categorical	By medication
Sleep medication	Categorical	By medication
Antidepressant	Categorical	By class (SSRI, SNRI, Other)
Other non-AD	Categorical	By class (Hormone,
		Antimigraine, Anti-convulsant)
Concomitant non-psychotropic		
medication		
NSAID	Categorical	By class
Other	Categorical	By class
Concomitant Therapy		
Psychotherapy	Categorical	Yes/No
Other	Categorical	By therapy

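### Neither per-protocol population has a concomitant-medication criterion, so the supporting analysis of TMS monotherapy can keep patients who start a prohibited psychotropic during Phase I

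*SAP*

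**What the plan says.** **The question.** Protocol 9.1 sets out to evaluate TMS as a monotherapy antidepressant. SAP Section 1.A says that "no antidepressant medications are permitted during the course of all three study Phases". Protocol 14.3 prohibits antidepressants, antipsychotics, stimulants, mood stabilizers and other CNS-active drugs on study, apart from a limited hypnotic and lorazepam allowance.

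**The per-protocol sets (SAP Section 3.C.3).** Both require consent, enrolment, satisfied entry criteria and efficacy assessments at Week 4 or Week 6. Population 1 adds that the subject "received at least 30 treatments within 6 weeks of treatment initiation of the Phase I acute treatment". Population 2 takes those who "completed all efficacy assessments at week 4 or week 6, and met the protocol requirements treatment compliance". The SAP then explains the last term: "The protocol defines treatment compliance as a subject cannot miss" three or more sessions in a row, or more than 20% of the acute sessions. Population 2 is named as the primary per-protocol set.

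**Their role.** The opening of SAP Section 4 makes the per-protocol population the supporting analysis for the primary and secondary outcomes. SAP Section 7.B (Table 6) also lists HAMD24 per protocol among the continuous secondary outcomes.

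**What is done with prohibited drugs.** SAP Section 9.A asks for a listing that gives "the proportion of patients who received any concomitant medications listed on the Excluded Medications List", and its Table 10 includes an antidepressant row by class. Neither is linked to an analysis population.

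**The concern.** In a trial of monotherapy against depression, starting an antidepressant departs from the treatment under test and can act on the same rating scale. A reader expects a per-protocol set to remove such patients. Here they can remain.

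SAP Section 3.C reports both populations to show that the findings are consistent. If the two agree, that agreement could be taken as support for TMS given alone, although the per-protocol set never imposed that condition. An excess of users on sham would tend to shrink the difference. An excess on active would credit drug effect to TMS.

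**Working it through.** The plan gives no figure on this point. The check is whether any rule in either document would remove a patient who starts a prohibited psychotropic after randomization and keeps attending.

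1. **Entry criteria.** Both sets require them, but the medication exclusion looks at entry. Protocol 11.3 excludes "Subjects currently on concurrent medication listed as excluded on the Concomitant Medication list (Appendix D"), and the synopsis ties the drug exclusion to the week before the baseline visit. A drug started in week 2 breaches neither.

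2. **Treatment compliance.** Protocol 14.2 defines non-adherence as missing three or more sessions in daily sequence or "missing more than 20% of the total number of treatment sessions occurring during the 6 weeks of acute treatment", with 30 sessions as full compliance. The allowance is 0.20 × 30 = 6 missed sessions, so 30 − 6 = 24 attended sessions can suffice for population 2 if no three consecutive ones are missed. Drug use does not enter the rule.

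3. **Withdrawal.** Protocol 11.5 lets the investigator withdraw a subject who does not comply with study procedures. It does not name prohibited medication. If the investigator did withdraw such a patient with three or more sessions left, and those sessions counted as missed, the patient would fail both sets. The rule is permissive, so it need not be applied.

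4. **The consequence stated in Protocol 14.3.** Overuse of the permitted hypnotics or lorazepam, or a new hormonal contraceptive, "may lead to excluding the subject from the study". This too is discretionary. The sentence states no consequence for starting an antidepressant, and it defines no analysis set.

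5. **Result.** A patient who starts a prohibited antidepressant in Phase I, is not withdrawn, completes the assessments and attends all 30 sessions meets every criterion of both populations. One who misses up to 6 sessions, never three in a row, still meets population 2.

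**Scale, for illustration only.** The documents give no rate of use. Assume that the share starting an antidepressant is 5% to 20% higher in one arm, and that each user gains 0.30 to 0.68 SD. Those two effect sizes are cited in the sample-size sections (Protocol 15.1, SAP Section 2.A) and come from treatment-naïve patients.
- Low: 0.05 × 0.30 = 0.015 SD
- High: 0.20 × 0.68 = 0.136 SD

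The sign depends on which arm has the excess. This is contamination of an all-patient difference. It does not estimate how far the per-protocol result would move if users were removed, which also depends on how their prognosis differs from that of non-users.

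**The case against.** The strongest case against the point is that these are openly attendance-based sets. Population 1 is called the completer population, and population 2 is preferred because it matches the protocol's treatment regimen. The analysis is supportive and takes no part in the success criteria of SAP Section 2.D. Investigators can withdraw non-compliant subjects, and SAP Section 9.A will show how many took excluded drugs. Removing users has its own cost, since starting a drug may reflect poor progress. If that were commoner on sham, exclusion would drop poor sham outcomes, and blinded classification would not prevent it.

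Much of this stands. It limits the weight of the point and shapes the fix. It does not supply the missing criterion.

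A reader might also infer three stronger things that the documents do not support.

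- *That nothing in the protocol acts on such use.* The non-compliance ground in Protocol 11.5 can reasonably be read to cover it.
- *That the SAP expects antidepressant use in Phase I.* Table 10 is a reporting shell for all phases, including six months of follow-up. An empty row is possible.
- *That the bias is material against the plan's 1.7-point limit.* Multiplying an assumed differential use by an assumed effect gives anything from 0.05 × 2 = 0.1 to 0.15 × 6 = 0.9 HAMD24 points, but every input is invented. The 1.7 to 5.5 point range belongs to the primary efficacy variable, which Table 6 specifies on the intent-to-treat sample. This gap does not touch that analysis.

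**Conclusion.** The omission is plain in the text, and no other section fills it. Neither per-protocol population conditions on concomitant medication, so the supporting analysis of monotherapy can include patients who were not on monotherapy. Discretionary withdrawal narrows the gap without closing it.

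The effect cannot be sized or signed from the documents, and it is nil if no such patients exist. The primary intent-to-treat analysis and the 1.7 to 5.5 point criterion are unaffected. What is at stake is the interpretation of the per-protocol results, including HAMD24 per protocol as a listed secondary outcome. The change is worth making because it is specific and cheap, but it does not bear on whether the trial succeeds.

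**What to change.** Add to per-protocol population 2 in SAP Section 3.C.3: 'and took no psychotropic or other CNS-active medication prohibited by Protocol 14.3, and did not exceed the Section 14.3 hypnotic/anxiolytic allowance, between the first Phase I treatment and the analysed Phase I assessment'.

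- Classify cases from the recorded administration dates, which SAP Section 9.A already requires, before treatment codes are released.
- Do not count use within the Section 14.3 allowance, or non-psychotropic drugs that merely carry an N code in Appendix D. Otherwise one dose of a cold remedy could remove a patient.
- Appendix D and Section 14.3 conflict in places. For example, Appendix D bars pseudoephedrine while Section 14.3 allows decongestants without psychotropic effects. These passages must be reconciled before cases are classified.
- Report the number excluded under this criterion by arm, and keep the intent-to-treat analysis as primary.

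The cost is one clause and a blinded listing review. The downside is a slightly smaller set that excludes patients on a post-randomization event that may reflect poor response. The SAP should say so beside the result.
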